5.6 Total Expected Duration of the Clinical Investigation

5.7 Expected Duration of Each Subject's Participation

Each subject will be followed for approximately 1 month after the MRI procedure. Participation will end after the 1 month follow-up visit.

5.8 Number of Subjects

To support the safety of the Infinity DBS system with MR Conditional labeling, up to 74 subjects will be enrolled in this study. Approximately 35 subjects will be included in each device configuration group (Leads Only and Full System). The total number of enrolled subjects assumes a 5% attrition rate following enrollment (e.g., due to subject unwilling to undergo DBS implant procedure, or for any other reason). Data from only one MRI procedure for each subject will be collected.

6.0 TREATMENT AND EVALUATION OF ENDPOINTS

6.1 Enrollment

Enrollment and baseline may take place in the same visit. The enrollment visit will take place in the clinic prior to the MRI procedure. The following activities are performed after the subject has been screened and must occur before any procedure/visit.

- The principal or delegated investigator is responsible for screening all potential patients to determine subject eligibility for the study.
- If a patient meets all inclusion criteria and does not meet any of the exclusion criteria, he/she is
 eligible for the study.
- The patient is enrolled in the study after signing the IRB/EC approved consent form.

Record enrollment information (date of consent and inclusion/exclusion information) in the hospital records and complete the enrollment form, preferably within 5 days of enrollment.

As soon as the patient signs the Subject Informed Consent Form, adverse events need to be reported according to the guidelines mentioned in this CIP [section 7.0].

In case the subject was consented to participate in the study, but is later found to not meet inclusion/exclusion criteria, and did not undergo an MRI procedure, the subject should be withdrawn and a withdrawal form must be completed. The subject will resume his/her regular standard of care with his/her physician.

In case the subject was consented to participate in the study and did undergo an MRI procedure, but does not meet inclusion/exclusion criteria, it is considered a protocol deviation. A protocol deviation form needs to be completed and the sponsor must be informed. The subject will be followed through the 1 month visit.

6.2 Baseline Data Collection

There is no minimum required time between implantation of the device and the MRI procedure. This will be determined by the physician based on the subject's standard of care. The following data will be collected at baseline:

- Subject demographics
- Medical condition for performing an MRI procedure
- Medical indication for having received/receiving DBS
- Adverse events
- Protocol deviations (if applicable)
- Withdrawal (if applicable)
- Device deficiency (if applicable)
- Product out of service data (if applicable)

6.3 MRI Procedure

The MRI procedure will take place at an appropriate facility. The MRI procedure must be performed according to the guidelines outlined in the MRI Procedure Information Clinician's Manual.

6.3.1 Pre-MRI/MRI Procedure Data Collection/Clinical Assessments (In clinic)

Subjects will be screened to ensure that they are eligible to undergo an MRI procedure. The following data will be collected before the MRI procedure:

- Subject eligibility for MRI procedure
- DBS lead(s) information
- Adverse events
- Protocol deviations (if applicable)
- Withdrawal (if applicable)
- Device deficiency (if applicable)
- Product out of service data (if applicable)

For subjects in the full system configuration group, the following additional data will be collected:

- DBS extension and DBS IPG information
- Success or failure of 'turn on' functionality of MRI mode
- Success or failure to 'turn on/off' functionality of the stimulation
- Success or failure to make adjustments to the stimulation amplitude
- Success or failure of device interrogation and download of IPG parameters
- Success or failure to obtain lead impedance measurements (only if the Clinician Programmer is being used to interrogate the IPG)

6.3.2 Immediate Post-MRI Procedure (In clinic, after the MRI procedure has been performed)

The following data will be collected after the MRI procedure:

- MRI scanner manufacturer/model
- Scan region (anatomic location)
- Subject position during MRI procedure
- Static field strength
- RF coil type
- RF power
 - o B1+RMS, head SAR, and/or whole body SAR, if applicable
 - Duration of each scan
- Total active scan time
- DICOM image files (de-identified), if available
- Adverse events
- Protocol deviations (if applicable)
- Withdrawal (if applicable)
- Device deficiency (if applicable)
- Product out of service (if applicable)

For subjects in the full system configuration group, the following additional data will be collected immediately after the MRI procedure:

- Success or failure of 'turn off' functionality of MRI mode
- Success or failure to 'turn on/off' functionality of the stimulation
- Success or failure to make adjustments to the stimulation amplitude
- Success or failure of device interrogation and download of IPG parameters Success or failure to obtain lead impedance measurements (only if the Clinician Programmer is being used to interrogate the IPG)

6.4 Follow-up Assessments

6.4.1 1 Month Post-MRI Procedure Follow-up (In clinic)

The only follow-up visit for all subjects in this study will be scheduled for 30 days \pm 14 days after the MRI procedure. The follow-up visit will be conducted in the clinic and data collection will include:

- For subjects with a full DBS system implanted (includes subjects in the full system configuration group and subjects in the leads-only group who had an IPG implanted and connected to at least one lead after the MRI procedure):
 - o Success or failure to 'turn on/off' functionality of the stimulation

Clinical Investigation Plan

- o Success or failure to make adjustments to the stimulation amplitude
- o Success or failure of device interrogation and download of IPG parameters
- Success or failure to obtain lead impedance measurements (only if the Clinician Programmer is being used to interrogate the IPG)
- Adverse events
- Protocol deviations (if applicable)
- Withdrawal (if applicable)
- Device deficiency (if applicable)
- Product out of service data (if applicable)

6.4.2 Unscheduled visit

Subjects may be asked or need to return to the clinic before the 1 month visit to assess various program parameters or undergo additional surgery to replace, reposition/revise or explant the DBS component(s) or system. This is considered an unscheduled visit. An IPG implant procedure for the Leads-Only group occurring after the MRI procedure is acceptable and will also be considered an additional surgery. If an unscheduled visit occurs, the following information will be recorded:

- Reason for visit
- Action taken
- Adverse events
- Session records, if (re)programmed
- Additional surgery information (if applicable)
- Protocol deviation (if applicable)
- Withdrawal (if applicable)
- Device deficiency (if applicable)
- Product out of service data (if applicable)

6.4.3 Non-Study MRI Procedures

In some cases, a non-study MRI procedure may be medically necessary. A non-study MRI procedure is defined as an MRI scan occurring after the study MRI procedure but prior to the 1 month follow-up visit. Non-study MRI procedures should be performed according to the center's standard of care.

For non-study MRI procedures, the same safety precautions outlined in the MRI Procedure Information Clinican's Manual should be followed. However, data for the non-study MRI procedures will not be collected within the study setting.

Clinical Investigation Plan

6.4.4 Schedule of Events

CIP Activity	Enrollment	Baseline	MRI visit		1 Month post-MRI Follow-	Unscheduled
			Pre-MRI/ MRI Procedure	Immediate Post- MRI Procedure	up (30 days ± 14 days after MRI procedure)	
Informed Consent Process	X					
Inclusion/Exclusion Criteria Check	X					
Demographics		X				
Medical condition indicated for MRI procedure		X				
Subject eligibility for MRI procedure			X			
Medical indication for DBS		X				
DBS Lead information			X			(X)
IPG and extension information			X*			(X)
MRI procedure			X			
DICOM image files				(X)		
MRI parameters				X		
Turn "on" of MRI mode			X*			
Turn "off" of MRI mode				X*		
"On/off" of stimulation			X*	X*	X**	
Adjustments to the stimulation amplitude			Х*	X*	X**	
Interrogation and download of IPG parameters			Х*	X*	X**	
Impedance testing			(X*)	(X*)	(X**)	
Session records			(X*)	(X*)	(X**)	(X**)
Adverse Events	(X)	(X)	(X)	(X)	(X)	(X)
Protocol Deviation	(X)	(X)	(X)	(X)	(X)	(X)
Withdrawal	(X)	(X)	(X)	(X)	(X)	(X)
Product Out of Service Data	(X)	(X)	(X)	(X)	(X)	(X)
Device Deficiency Information	(X)	(X)	(X)	(X)	(X)	(X)

X* = for subjects in the full system configuration group

X** = for subjects with a full DBS system implant (includes subjects in the full system configuration group and subjects in the leads-only group who had an IPG implanted and connected to at least one lead after the MRI procedure)

7.0 ADVERSE EVENTS

To comply with worldwide standards and guidelines on clinical investigation adverse event reporting, the Sponsor has adopted uniform and worldwide applicable standard definitions and reporting timelines to be used and adhered to by the investigators.

7.1 Definition

7.1.1 Adverse Event

An adverse event (AE) is any untoward medical occurrence, unintended disease or injury, or untoward clinical signs (including abnormal laboratory findings) in subjects, users or other persons, whether or not related to the medical device under investigation.

Note 1: This definition includes events related to the medical device under investigation or the comparator.

Note 2: This definition includes events related to the procedures involved.

Note 3: For users or other persons, this definition is restricted to events related to medical devices under investigation.

7.1.2 Serious Adverse Event

If the AE meets any of the criteria below, it is regarded as a serious adverse event (SAE).

- a) Led to a death,
- b) Led to a serious deterioration in health of the subject, that either resulted in
 - 1. a life-threatening illness or injury, or
 - 2. a permanent impairment of a body structure or a body function, or
 - 3. in-patient hospitalization or prolongation of existing hospitalization, or
 - 4. medical or surgical intervention to prevent life threatening illness or injury or permanent impairment to a body structure or a body function, or
 - 5. chronic disease
- c) Led to fetal distress, fetal death or a congenital abnormality or birth defect.

Note: A planned hospitalization for pre-existing condition, or a procedure required by the CIP, without a serious deterioration in health, is not considered to be an SAE.

7.2 Device and Procedure Relationship

Determination of whether there is a reasonable possibility that the device under investigation or the DBS procedure (if applicable) caused or contributed to an AE is to be determined by the Investigator and recorded on the appropriate case report form (CRF). Determination should be based on assessment of temporal relationships, evidence of alternative etiology, medical/biologic plausibility, and patient condition (pre-existing condition).

Sensation of bodily warmth	During and < 1 hour post MRI scan			
Hearing impairment	< 24 hours post MRI scan			
Body stiffness related to immobility	< 48 hours post MRI scan			

7.4 Adverse Event

7.4.1 Adverse Event Reporting

General AE Reporting

Safety surveillance and reporting starts as soon as the patient is enrolled in the clinical investigation. Safety surveillance and reporting will continue until the one month follow-up visit has been performed, the subject is deceased, the subject concludes participation in the clinical investigation or the subject withdraws from the clinical investigation, whichever comes first. All adverse event data will be collected throughout the time period defined above and will be reported to the Sponsor on a CRF. Additional information with regard to an adverse event should be updated within the appropriate CRF.

Unchanged, chronic, non-worsening or pre-existing conditions are not AEs and should not be reported.

An offline form will be made available to allow the investigator to report SAEs in the event the entry cannot be made in the electronic data capture (EDC) system. This does not replace the EDC reporting system. All information must still be entered in the EDC system as soon as feasible.

SAE Reporting

The investigator should report all SAEs to the Sponsor as soon as possible but no later than outlined below.

Clinical Site	Reporting timelines
All Sites	SAEs must be reported to the Sponsor no later than 3 calendar days from the
	day the site personnel became aware of the event or as per the site's local
	requirements, if more stringent than 3 calendar datys.

The date the site staff became aware the event met the criteria of an SAE must be recorded in the source document. The Investigator will further report the SAE to the local IRB/EC according to the local IRB/EC reporting requirements.

Reportable events to the sponsor are considered:

- All serious adverse events regardless of relatedness to the device and/or implant procedure
- All device- or implant procedure-related adverse events
- All MRI-related adverse events

Refer to the specific device manuals for the adverse events that are associated with implanting or using the neurostimulation system for DBS and for MRI related adverse events.

7.4.2 Device Deficiency/Malfunction Reporting

All device deficiencies/malfunctions should be reported on the appropriate CRF. The investigator should report all device deficiencies/malfunctions to the Sponsor as soon as possible but no later than 3 calendar days from the day the site personnel became aware of the event or as per the site's local requirements, if more stringent than 3 calendar days.

Device deficiencies/ malfunctions should be reported to the IRB/EC per the site's local requirements.

An offline form will be made available to allow the investigator to report device deficiencies/malfunctions in the event that the entry cannot be made in the EDC system. This does not replace the EDC reporting system. All information must still be entered in the EDC system as soon as feasible.

7.4.3 Adverse Event Reporting to Country Regulatory Authorities by the Sponsor

The Sponsor will report SAEs to the country regulatory authority, per local requirements.

7.4.4 Procedure for Recording and Reporting Subject Death

Should death occur, the investigator is requested to record death information in the hospital records and immediately document the information on the AE case report form and submit to Sponsor. The investigator should report the death as soon as possible and per the reporting timeline for SAEs in section 7.4.1.

• All efforts to obtain the details about the circumstances surrounding the patient death should be made by the Investigator.

The subject's death is an outcome of an AE and an early conclusion of the subject's participation in the clinical investigation. Therefore, the Investigator is required to complete the Withdrawal form.

8.0 STATISTICAL CONSIDERATIONS

The following section describes the statistical methods for the clinical investigation. Additional details on statistical analyses, including justification of clinical investigation design, and analysis of additional endpoints, may be maintained in a separate Statistical Analysis Plan (SAP).

8.1 Analysis Populations

All subjects who have signed a Subject Informed Consent Form will be considered enrolled in the clinical investigation. However, it is anticipated that there will be subjects who are enrolled in the study, but will not be included in the primary endpoint analysis, such as:

- Subjects who are enrolled, but do not meet inclusion criteria or meet exclusion criteria and do not undergo and MRI procedure; these subjects will be withdrawn from the study.
- Subjects who are enrolled, but do not undergo an MRI procedure; these subjects will be withdrawn from the study.

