5.5 Subject Withdrawal

Each enrolled subject shall remain in the clinical investigation until completion of the required follow-up period; however, a subject's participation in any clinical investigation is voluntary and the subject has the right to withdraw at any time without penalty or loss of benefit. Conceivable reasons for discontinuation may include, but not be limited to, the following:

- Subject death (cause must be documented)
- Subject does not meet the inclusion/exclusion criteria and does not require additional follow-up
- Subject voluntary withdrawal
- Subject non-compliance
- Subject's participation is terminated by the PI or co-investigator
- Subject lost-to follow-up as described below
- Subject's follow-up is terminated according to Section 3.3.

The Sponsor must be notified of the reason(s) for subject discontinuation. The site will provide this information to the Sponsor. Investigators must also report this to their respective IRB/EC as defined by their institution's procedure(s).

No additional follow-up will be required or data recorded from subjects once withdrawn from the clinical investigation, except for the status (deceased/alive) at the time of withdrawal, if not previously collected.

However, if a subject withdraws from the investigation due to problems related to the safety or performance of the device under investigation, the investigator shall ask for the subject's permission to follow his/her status/condition outside of the clinical investigation as appropriate.

Lost-to-Follow-up

A subject is considered lost-to-follow-up if the subject does not adhere to the scheduled follow-up visit but has not explicitly requested to be withdrawn from the clinically study. Site personnel shall make all

reasonable efforts to locate and communicate with the subject (and document these efforts in the source documents), including the following, at each contact time point:

- A minimum of two telephone calls on different days over the specified follow-up windows to contact the subject should be recorded in the source documentation, including date, time and initials of site personnel trying to make contact.
- If these attempts are unsuccessful, a letter (certified if applicable) should be sent to the subject.
- If a subject misses the follow-up contact time point, it will be considered a missed visit. If the
 subject misses their 1-month follow-up visit and the above-mentioned attempts at communicating

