8.2.2 Secondary Endpoint Analysis

The following secondary endpoints will be analyzed for subjects who undergo an MRI procedure with a full system configuration. The endpoint "Rate of successful ability to obtain lead impedance measurements" will include only those subjects who had their IPG interrogated using the Clinician Programmer. Data (success or failure) for these endpoints will be collected immediately after the MRI procedure.

- Rate of successful MRI mode 'turn on/off' functionality of the MRI mode
- Rate of successful 'turn on/off' functionality for the stimulation
- Rate of successful adjustments to the stimulation amplitude
- Rate of successful interrogation and download of the IPG parameters
- Rate of successful ability to obtain lead impedance measurements

Rates will be reported as the percentage of subjects in which the device functionality could be successfully completed.

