# 2.9 Handling of Missing Data

No imputation techniques will be implemented in the analysis. The secondary endpoints will be evaluated in subjects who undergo an MRI procedure with a full system configuration. Subjects who don't have the IPG testing complete immediately after MRI procedure will be excluded from the related endpoint analysis.

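### The MRI-mode turn-on rate counts only scanned subjects, so a turn-on failure that leads to no scan would be left out of it

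*Protocol*

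**What the plan says.** One secondary endpoint is the rate at which MRI mode is successfully turned on and off (Protocol 4.2, SAP 1.4.2). The two halves are tested at different times. Protocol 6.3.1 places turn-on before the scan: "For subjects in the full system configuration group, the following additional data will be collected", and the list that follows includes success or failure of turning MRI mode on. Protocol 6.3.2 places turn-off immediately after the scan. The schedule of events in 6.4.4 agrees.

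The analysis population is defined by the scan. Protocol 8.2.2 states: "The following secondary endpoints will be analyzed for subjects who undergo an MRI procedure with a full system configuration". SAP 2.3.2 says the same, and SAP 2.9 repeats it: "The secondary endpoints will be evaluated in subjects who undergo an MRI procedure with a full system configuration". SAP 2.9 then narrows the population further: "Subjects who don't have the IPG testing complete immediately after MRI procedure will be excluded from the related endpoint analysis". Protocol 8.2.2 also fixes the timing: "Data (success or failure) for these endpoints will be collected immediately after the MRI procedure". The summary added in SAP 3.5 and 6.0 is again taken at the post-MRI visit. The SAP plans no imputation (2.9) and no sensitivity analysis (2.13).

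Protocol 8.1 adds, among the examples of subjects left out of the primary analysis: "Subjects who are enrolled, but do not undergo an MRI procedure; these subjects will be withdrawn from the study".

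**The concern.** Whether a subject is scanned is settled after turn-on has been attempted, and may depend on the result. A turn-on rate computed only in scanned subjects is therefore conditioned on a later event that the outcome itself can influence. A subject whose MRI mode will not turn on, and who for that reason is never scanned, is in neither the numerator nor the denominator. Moving the data collection earlier would not cure this. The problem is who is counted, not when.

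MRI mode is the one design difference from the predicate system that Protocol 15.6 names, and the results go to the notified body (Protocol 3.0). A reported 100% could be read there as evidence that activation always works, when the rate was not built to show the failure that would matter most for activation.

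**Working it through.** **The plan's own figure.** Protocol 5.8 gives about 35 subjects per configuration group, 5% attrition and up to 74 enrolled. Two groups make 70, and 70 / (1 − 0.05) = 73.7, which rounds up to 74. Per group, 35 / 0.95 = 36.8, which rounds up to 37. The stated total reproduces. The documents give no failure rate for MRI-mode activation.

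**Who is counted.** Take each possible course for a full-system subject in turn:
- Turn-on works and the scan is done: counted.
- Turn-on fails, the failure is resolved and the scan is done: still in the denominator. The documents do not say whether the failed attempt is scored as a failure.
- Turn-on works, the scan is done and turn-off fails: counted against the endpoint.
- Turn-on fails and the scan is never done: not counted at all.

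Only the last course is lost.

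**Formula.** Let N be the full-system subjects in whom turn-on is attempted, and k those who fail and are not scanned. Assume that turn-on works in everyone who is scanned. Then:
- Rate in scanned subjects: (N − k) / (N − k) = 100% for any k below N.
- Rate in all attempted: (N − k) / N.
- Difference: k / N.

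**Illustration.** N = 37 is half of the 74 enrolled. The values of k are assumptions. Intervals are exact 95% Clopper-Pearson, the type named in SAP 2.2.2.

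| k | Scanned only | All attempted |
|---|---|---|
| 1 | 36/36 = 100% (90.3 to 100) | 36/37 = 97.3% (85.8 to 99.9) |
| 2 | 35/35 = 100% (90.0 to 100) | 35/37 = 94.6% (81.8 to 99.3) |
| 3 | 34/34 = 100% (89.7 to 100) | 34/37 = 91.9% (78.1 to 98.3) |
| 5 | 32/32 = 100% (89.1 to 100) | 32/37 = 86.5% (71.2 to 95.5) |

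With N = 35 and k = 2, the figures are 33/33 = 100% against 33/35 = 94.3% (80.8 to 99.3), so the choice of N matters little. With k = 0 the two definitions agree.

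**The case against.** The strongest objection is that the causal step lies outside the documents. No section says that a failed activation cancels the scan. Protocol 6.3 only requires the scan to follow the Clinician's Manual, which is not available. This stands, and the conclusion has to be conditional on it.

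A second objection is that for stimulation on/off, amplitude adjustment, interrogation and impedance, restriction to scanned subjects is the declared question: does the device work after MRI exposure? A pre-scan failure is not an effect of MRI. This also stands. For impedance, Protocol 6.3.1 records the pre-scan test only when the Clinician Programmer is used, so a scan can evidently go ahead without it. The point is confined to the turn-on half of one endpoint.

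Third, a reader might infer that the withdrawal rule in Protocol 8.1 causes the loss. It does not. That sentence concerns the primary analysis, and an unscanned subject would be outside the function rates without it. Nor does withdrawal erase earlier data: Protocol 5.5 stops further recording ("No additional follow-up will be required or data recorded from subjects once withdrawn from the clinical investigation", apart from vital status) and does not call for deletion of what is already held.

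Fourth, the failure is not lost from the record. The pre-MRI case report form holds it, Protocol 7.4.2 requires deficiencies to be reported, and SAP 3.3 summarizes reasons for early termination. That is true, but none of these feeds the rate. The SAP text describes no table of pre-scan function results or of deficiencies. The table mock-ups it mentions are not among the documents, so their content cannot be judged.

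Finally, N = 37 uses up the whole attrition allowance, and the example of attrition in Protocol 5.8 is a subject unwilling to be implanted, who would never reach a device check. This is fair, and the table is an illustration only.

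**Conclusion.** The concern holds in a limited form. As written, the turn-on component of the MRI-mode rate omits any turn-on failure that leads to the scan not being done, and is biased towards 100% to that extent. The size is k / N: with 1 to 5 such failures in 37 attempts, 2.7 to 13.5 percentage points. This rests on the assumption that a turn-on failure can stop the scan. The number of failures is unknown, and zero is compatible with the documents.

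A reader might go further and infer that the endpoint must come out at 100% whatever the device does. The documents do not support that: turn-off failures still count, and a device that fails and is later scanned remains in the denominator. Nor does the point reach the study's conclusion. The function endpoints are descriptive and secondary with no acceptance threshold, and success depends on the primary endpoint alone (Protocol 8.9, SAP 2.7).

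**What to change.** In Protocol 8.2.2 and SAP 2.3.2 and 2.9:
- Split the MRI-mode endpoint and report turn-on separately. Its denominator is all enrolled full-system subjects in whom activation was attempted at the pre-MRI check, scanned or not. Failure to activate counts as a failure.
- Keep turn-off and the other post-MRI functions in scanned subjects.
- Report beside the turn-on rate the number of scans not done for device reasons.
- Word SAP 2.9 so that its exclusion for incomplete post-scan testing does not apply to turn-on.

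Protocol 8.1 needs no change. The turn-on result is already collected under Protocol 6.3.1, so the cost is wording only, with no new procedure or visit. The downside is that the reported rate may be slightly less favourable.
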